Appendix 4. Columbia–Suicide Severity Rating Scale

[figure not shown]

[figure not shown]

[figure not shown]

[figure not shown]

[figure not shown]
C-SSRS – Since Last Visit Version

[figure not shown]

[figure not shown]

[figure not shown]
Appendix 5. Prohibited Concomitant Medication List

[figure not shown]
- Aminoglycoside antibiotics
- Baclofen
- Benzodiazepines for anti-spastic indication
- Botulinum toxin therapy of any serotype
- Cannabinoids
- Carisoprodol
- Chlormezanone
- Curariform drugs
- Dalfampridine
- Dantrolene
- Gabapentin for anti-spasticity indication
- Meprobamate
- Methocarbamol
- Neuroleptics
- Orphenadrine
- Cyclobenzaprine
- Tizanidine
- Tolperisone

[figure not shown]
Appendix 6. Urinary Symptom Profile Questionnaire

[figure not shown]

[figure not shown]

Appendix 7. [REDACTED]

Appendix 8. Summary of Changes

The following changes have been made to Protocol CLN.OS440-3005.PR.A02.USA as Country-Specific Amendment 2, applicable to the United States (US) only:

SECTION(S)	CHANGE/RATIONALE
Entire Document	Made style and editorial corrections and clarifications, fixed errors, added revised protocol number, and added hyperlinks.
Title Page	Added protocol versions history.
Sections 4.1, 5.1, 6.1 (new), 6.2, 7.7 and Table 1 footnote	Changed the Screening duration for de novo subjects from a minimum of 21 days to a maximum of 21 days,
Section 5.1	Added the TNmAS-MAL to the inclusion criteria for de novo subjects: “ De novo subjects being considered for enrollment must have spasticity due to MS as shown by a TNmAS-MAL score ≥ 2 .”
Section 5.2	Changed exclusion criterion 12 by replacing “Baseline” with “Screening”: “Subject has clinically significant abnormal laboratory values, in the opinion of the investigator at Screening (at Visit 6 for rollover subjects).”
Section 6.1 (now 6.2), Section 9, and Table 1	Moved the majority of the assessments for de novo subjects from Baseline to Screening: “For de novo subjects being considered for enrollment, a Screening visit should occur a maximum of 21 days prior to Baseline to allow for any concomitant medication wash-out required for Inclusion Criterion 6. For de novo subjects, the following procedures will be done at this Screening visit: informed consent, inclusion/exclusion criteria, withdrawal of anti-spasticity medication, demography, medical/surgical history, physical examination, height, weight, vital signs, hematology/serum chemistry/urinalysis, ECG, serum pregnancy test, C-SSRS, TNmAS-MAL, USP, EDSS, and recording of concomitant medications. For de novo subjects, the following assessments and procedures will be performed at the Baseline visit: assign enrollment number, vital signs, urine pregnancy test, C-SSRS, TNmAS-MAL, PGIC, USP, dispensing of study medication, recording of AEs and concomitant medications, and scheduling/confirmation of the next study visit.”
Section 6.1 (now 6.2), 6.3 (now 6.4), 6.5 (now 6.6), Section 8.1, and Table 1 footnote	Removed the Patient Global Impression of Change (PGIC) at Visit 4 (Week 28).
Sections 7.1.1, 7.9, and 12.4	Changed the rule requiring subjects who miss 7 or more consecutive days of dosing to be discontinued; the new rule requires discontinuation only if the subject misses 7 or more consecutive days of dosing AND has taken less than 80% of their doses of study medication in a 42-day (6-week) period.
Sections 1 and 9.7.3	Changed name and contact information for one of the Medical Monitors for SAE reporting.
Appendix 8	Added new Appendix 8 Summary of Changes to summarize the changes made to the original protocol with Amendment 2.

The following changes have been made to Protocol CLN.OS440-3005.PR.A01 as Amendment 1:

SECTION(S)	CHANGE/RATIONALE
Entire Document	Made editorial corrections and clarifications, fixed errors, added revised protocol number, and added hyperlinks.
Title Page	Added protocol versions history.
Section 9.6.2	Corrected the mistake in the original protocol regarding a 4-point change in total USP score by replacing “A reduction of 4 points...” with “An increase of 4 points...”
Appendix 8	Added new Appendix 8 Summary of Changes to summarize the changes made to the original protocol with Amendment 1.

2. LIST OF ABBREVIATIONS AND DEFINITION OF TERMS

Only abbreviations and terms relevant to the SAP are repeated herein. The reader is referred to the protocol for the complete and comprehensive list of abbreviations and definitions of terms for the study.

Abbreviation	Definition
ADaM	Analysis data Model
AE	Adverse event
AERT	Arbaclofen extended-release tablets
CDISC	Clinical Data Interchange Standards Consortium
CRF	Case report form
C-SSRS	Columbia–Suicide Severity Rating Scale
DSMB	Data Safety Monitoring Board
ECG	Electrocardiogram
eCRF	Electronic case report form
EDSS	Expanded Disability Status Scale
FDA	Food and Drug Administration
ICH	International Conference on Harmonization
IRB	Institutional Review Board
IRT	Interactive Response Technology (system)
mAS	Modified Ashworth Scale
MedDRA	Medical Dictionary for Regulatory Activities
MS	Multiple Sclerosis
PGIC	Patient Global Impression of Change
PT	Preferred term
SAE	Serious adverse event
SAP	Statistical Analysis Plan
SD	Standard deviation
SDTM	Study Data Tabulation Model
SOC	System organ class
TEAE	Treatment-emergent adverse event
TNmAS-MAL	Total Numeric-Transformed Modified Ashworth Score – Most Affected Limb
TNmAS-TL	Total Numeric-Transformed Modified Ashworth Score – Total Limbs
USP	Urinary Symptom Profile - USP [®] questionnaire
WHO	World Health Organization
WHO-DD	World Health Organization – Drug Dictionary

3. INTRODUCTION

3.1. Preface

This document presents a statistical analysis plan (SAP) for Osmotica Pharmaceutical's Protocol OS440-3005 (*An Open-Label Study to Evaluate the Long-Term Safety of Arbaclofen Extended-Release Tablets in Multiple Sclerosis Patients with Spasticity*).

Reference materials for this statistical plan includes the protocol OS440-3005 (CLN.OS440-3005.PR.A01 Dated: 03 OCT 2017).

The SAP described hereafter is an *a priori* plan. The SAP will be finalized and approved prior to locking of the study database.

For the reasons stated here, the conduct of the study in the field is considered to be independent of any study outcome that might materialize upon enactment of the currently proposed statistical plan.

3.2. Purpose of Analyses

The purposes of the planned analyses described in this SAP are to assess the safety and efficacy of oral arbaclofen extended-release tablets (AERT) in MS subjects with spasticity. Results from the analyses completed will be included in the final clinical study report for Study OS440-3005, and may also be utilized for regulatory submissions, manuscripts, or other clinical development activities.

Post-hoc exploratory analyses not identified in this SAP may be performed to further examine the study data. These analyses will be clearly identified, where appropriate, in the final clinical study report. Additional analyses not prospectively identified in this SAP may also be completed for publications, or regulatory or funding inquiries. These analyses, if performed, may not be reported in the clinical study report but will be fully documented in the document containing the additional analyses.

3.3. Summary of Statistical Analysis Changes to the Protocol

The analyses described in this analysis plan are consistent with the analyses described in the study protocol.

4. STUDY OBJECTIVES AND ENDPOINTS

4.1. Study Objectives

4.1.1. Primary Objective

The primary objective of this study is to evaluate the long-term safety and tolerability of AERT in subjects with spasticity due to MS.

4.1.2. Secondary Objectives

The secondary objectives are to:

- Assess the Patient Global Impression of Change (PGIC) over 1 year.
- Assess the Total Numeric-transformed modified Ashworth Scale score of the most affected limb (TNmAS-MAL) over 1 year.
- Assess the Expanded Disability Status Scale (EDSS) over 1 year.

4.2. Study Endpoints

4.2.1. Safety Endpoints

Safety endpoints include the following:

- Adverse events
- Vital signs
- Clinical laboratory tests
- 12-lead electrocardiograms (ECGs)
- Urinary Symptom Profile - USP© questionnaire (USP)
- Columbia-Suicide Severity Rating Scale (C-SSRS)

4.2.2. Efficacy Endpoints

Efficacy endpoints include the following:

- Patient Global Impression of Change (PGIC)
- Total Numeric-Transformed Modified Ashworth Score – Most Affected Limb (TNmAS-MAL)
- Total Numeric-Transformed Modified Ashworth Score – Total Limbs (TNmAS-TL)
- Expanded Disability Status Scale (EDSS)

5. STUDY METHODS

5.1. General Study Design and Plan

As background for the statistical methods presented below, this section provides an overview of the study design and plan of study execution. The protocol is the definitive reference for all matters discussed in what follows.

This is a multicenter, open-label, long-term extension study to evaluate the safety and tolerability of oral AERT in subjects with spasticity due to MS. Subjects from the double-blind study (Study OS440-3004) may rollover into this open-label extension study, as well as de novo subjects, provided that all inclusion and none of the exclusion criteria are met.

Eligible de novo subjects will undergo an at least 21-day washout period for withdrawal of all medications used for anti-spasticity and/or muscle relaxation prior to enrolling in this open-label study. There will be a 9-day titration period, then a 52-week maintenance period, followed by a 2-week taper period.

[Figure 1](#) presents the timeline diagram for the study. [Figure 2](#) presents the open-label dosing regimen flowchart, including titration and taper doses, to be used during the study. Once the subject has reached the maintenance dose, they will remain on that dose for approximately 1 year. The maintenance dose will be the highest tolerated dose not exceeding 80 arbaclofen mg per day.

The schedule of assessments is presented in [Table 1](#).

Figure 1 **Timeline Diagram**

[figure not shown]
[figure not shown]

Figure 2 Flowchart of Open-Label Dosing Regimen

At the end of treatment, a 2-week taper period will take place from Weeks 54 to 56. Subjects who discontinue early should also follow the 2-week taper period.

Table 1 Schedule of Assessments

Assessment or Procedure	Baseline ¹	Visits							Final Visit ²
Study Visit	(V6 of prior DB Study)	1	2	3	4	5	6	7 (telephone visit)	8
Study Week	0 (±3 days)	2 (±3 days)	6 (±5 days)	14 (±5 days)	28 (±5 days)	42 (±5 days)	54 (±3 days)	56 (±5 days)	60 (±3 days)
Written informed consent	X								
Inclusion and exclusion criteria	X								
Withdrawal anti-spasticity medication	X								
Assign enrollment number	X								
Demography	X								
Medical/surgical history	X								
Physical examination	X								
Height	X								
Weight	X				X				X
Vital signs ³	X	X	X	X	X	X	X	X	X
Hematology/serum chemistry/urinalysis	X		X	X	X	X	X	X	X
Electrocardiogram	X				X				X
Pregnancy test ⁴	X	X	X	X	X	X	X	X	X
C-SSRS	X	X	X	X	X	X	X	X	X
TNmAS-MAL ⁵	X				X				X
EDSS	X				X				X
PGIC ⁶	X				X				X
USP [®] questionnaire	X	X	X	X	X	X	X	X	X
Dispense study medication	X	X	X	X	X	X	X ⁷		
Collect unused study medication		X	X	X	X	X	X		X
Adverse event assessment	X	X	X	X	X	X	X	X	X
Concomitant medications/therapies	X	X	X	X	X	X	X	X	X
Schedule/confirm next study visit	X	X	X	X	X	X	X	X	

C-SSRS = Columbia–Suicide Severity Rating Scale; DB = double-blind; EDSS = Expanded Disability Status Scale; FV = final visit; PGIC = Patient Global Impression of Change; TNmAS-MAL = Total Numeric-transformed modified Ashworth Scale score of the most affected limb; USP = Urinary Symptom Profile.

(footnotes on next page)

Table 1 - Footnotes:

1. Baseline for the study will be conducted at the same time as Visit 6/Day 92 (Final Visit) of Study OS440-3004 for subjects willing to continue into this study. All assessments performed at Visit 6/Day 92 (Final Visit) of Study OS440-3004 should not be repeated but should be recorded as the same assessments at Baseline for this study.

Note: For *de novo* subjects being considered for enrollment, a Screening visit (not shown in Table 1) should occur a maximum of 21 days prior to Baseline to allow for any concomitant medication wash-out required for Inclusion Criterion 6. For *de novo* subjects, the first three procedures listed under Baseline (ie, informed consent, inclusion/exclusion criteria, and withdrawal of anti-spasticity medication) will be done at this Screening visit, as well as a serum pregnancy test (see footnote 4 below). All other baseline assessments and procedures listed will be performed at the Baseline visit for *de novo* subjects.

2. If a subject prematurely withdraws from the study, the subject should taper from study medication as described in Protocol Section 7.1 and all evaluations described under Visit 8/Week 60 (Final Visit) must be performed.
3. Vital signs will be measured with the subject in a supine position and in a standing position 3 minutes after the supine assessment is completed. Body temperature and respiratory rate will be measured only during the supine assessment.
4. For *de novo* subjects, premenopausal women of childbearing potential must have a negative serum pregnancy test within 21 days before Baseline. Urine pregnancy testing will be performed for all female subjects at the other visits as noted.
5. The TNmAS-MAL assessment will be performed prior to any scheduled lab draws. The most affected limb will be determined by the investigator.
6. The PGIC will not be done at Baseline for *de novo* subjects.
7. At the end of treatment, a 2-week taper period will take place from Weeks 54 to 56. Subjects who discontinue early should also follow the 2-week taper period.

5.2. Randomization and Blinding

Not applicable, this is an open-label, non-randomized study.

5.3. Analysis Variables

Variables to be analyzed include demographics and baseline characteristics, safety variables (adverse events, vital signs, clinical laboratory investigations, ECGs, USP questionnaire, and C-SSRS), and efficacy variables (PGIC, TNmAS-MAL, TNmAS-TL, and EDSS). See Section 8 of the protocol for further details on the efficacy variables. Derived variables from study endpoints are described with the sections describing the analyses for these endpoints.

6. SAMPLE SIZE

In total, approximately 300 subjects are to be enrolled in this study (ie, both rollover and de novo subjects). It is anticipated that approximately 50% of subjects randomized into the double-blind study (Study OS440-3004) may rollover into this open-label study. In the US only, up to 50 subjects may enroll into Study OS440-3005 without rolling over from Study OS440-3004.

The number of subjects at each site will be determined primarily by the rate of recruitment in Study OSS440-3004. No statistical rationale for subject number is provided.

The sponsor has previously completed a 1-year, open-label safety study (Study OS440-3003 using the 40-mg per day dose of arbaclofen. In Study OS440-3003 a total of 148 subjects were treated for 12 months. Study OS440-3005 is designed to enrich the existing safety database and provide long-term safety and tolerability data at the maximum daily dose of 80 mg/day. Target recruitment for Study OS440-3005 includes at least 100 subjects treated at 6 months and 50 subjects treated for 1 year at 80-mg per day.

7. GENERAL CONSIDERATIONS

7.1. Analysis Populations

There will be two (2) analysis populations defined for this study.

7.1.1. Screened Population (SCREEN)

Subjects who provide informed consent will be members of the screening population. The screening population will include the total number of subjects who were considered for this study (rollover and *de novo*), regardless of participation.

7.1.2. Safety Population (SP)

Includes all subjects who receive at least one dose of open-label study treatment and have at least one post-dose visit. This population will be used for all safety and efficacy analyses.

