Note: For *de novo* subjects being considered for enrollment, a Screening visit should occur a maximum of 21 days prior to Baseline to allow for any concomitant medication wash-out required for Inclusion Criterion 6. For *de novo* subjects, only the following assessments and procedures will be performed at the Baseline visit: assign enrollment number, vital signs, urine pregnancy test, C-SSRS, TNmAS-MAL, PGIC, USP, dispensing of study medication, recording of AEs and concomitant medications, and scheduling/confirmation of the next study visit.

2. If a subject prematurely withdraws from the study, the subject should taper from study medication as described in Section 7.1 and all evaluations described under Visit 8/Week 60 (Final Visit) must be performed.
3. Vital signs will be measured with the subject in a supine position and in a standing position 3 minutes after the supine assessment is completed. Body temperature and respiratory rate will be measured only during the supine assessment.
4. For *de novo* subjects, premenopausal women of childbearing potential must have a negative serum pregnancy test within 21 days before Baseline. Urine pregnancy testing will be performed for all female subjects at the other visits as noted.
5. The TNmAS-MAL assessment will be performed prior to any scheduled laboratory draws. The most affected limb will be determined by the investigator.
6. At the end of treatment, a 2-week taper period will take place from Weeks 54 to 56. Subjects who discontinue early should also follow the 2-week taper period.

Figure 1: Timeline Diagram, Study OS440-3005

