11.5 Safety Endpoints

Safety endpoints will be reported on the Safety population. Subjects will be reported according to the treatment they actually received. Safety assessment will be based on descriptive statistics and individual subject listings. No statistical tests will be performed for any of the safety assessments.

All reported AEs will be mapped to the Medical Dictionary for Regulatory Activities (MedDRA) system organ classifications (SOCs) and preferred terms (PTs). If a subject reports multiple events of a single PT, the greatest severity and strongest investigator assessment of relationship to study treatment will be assigned to that PT. Should an event have a missing severity or relationship, it will be classified as having the highest severity and/or strongest relationship to study drug. Summaries of treatment-emergent AEs (TEAEs) will include any AEs reported beginning with the first dose of study treatment on Day 1. The occurrence of TEAEs will be summarized by treatment group using SOCs, PTs, and severity. Separate summaries of treatment-emergent SAEs, TEAEs considered related to study treatment, and events leading to the discontinuation of study drug will be generated.

Descriptive summaries of vital signs, clinical laboratory results, USP results, and the C-SSRS results will be presented by study visit and treatment group. The number and percentage of subjects with treatment-emergent clinical laboratory abnormalities will be summarized by treatment group. Normal range clinical laboratory shifts from baseline to end of study will be summarized by treatment group.

Concomitant medications will be coded using the World Health Organization (WHO) dictionary. These data will be summarized by treatment group. Previous and concomitant medications will be presented in a data listing.

Subject disposition will be presented for all subjects. The numbers of subjects who complete the study and who discontinue early from the study will be provided. The reasons for early discontinuation will also be presented.

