12.4 Withdrawal of Subjects

Withdrawn subjects are those who do not complete all evaluations and procedures outlined in the protocol. Subject withdrawal requires a 2-week dose taper. A subject will be considered to have discontinued prematurely if he/she withdraws prior to completing Visit 8 (Final Visit). If a subject misses 7 consecutive days AND has taken less than 80% of their doses of study medication in a 42-day (6-week) period, then the subject must be discontinued. Subjects may also be withdrawn from the study because of any of the following:

- **Adverse Event:** An AE that, in the opinion of the investigator or Sponsor, suggests that continued participation in the study is not in the subject's best interest for safety reasons (also see [Section 10](#)). All AEs that are present when the subject withdraws from the study will be followed as described in [Section 9.7.4](#).
- **Medical Condition:** Any medical condition that, in the investigator's judgment, would increase the risk or interfere with the evaluation of study objectives.
- **Lost to Follow-up:** Confirmed at minimum by two phone calls and a traceable letter without answer.
- **Subject Request:** Subject requests for any reason to be withdrawn or withdraws his/her consent. Every effort should be made to determine the reason for the withdrawal request (e.g., AE, lack of efficacy, scheduling issues, etc.).
- **Protocol Deviation:** A subject may be withdrawn from the study at the discretion of the investigator or Sponsor due to poor compliance with protocol requirements that may compromise the study results or subject safety.
- **Enrollment in Another Study:** Enrollment in other protocols involving research drugs, medical devices, or surgeries.
- **Other Anti-spasticity Treatment:** Starting any other pharmacological anti-spasticity treatment during the study.

- **Relapse:** Subjects who experience an acute MS exacerbation/relapse (symptoms including but not limited to visual disturbance, dizziness, tingling, or extreme fatigue lasting greater than 24 hours and occurring at least 30 days after a previous relapse) requiring immediate therapy or adjustment in disease-modifying medication dose (e.g., oral or intravenous high-dose steroid therapy).

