- **Other:** Other reasons include but are not limited to: Investigator decision that it is in the subject's best interest to be withdrawn, administrative reasons, relocation of subject, etc. If a subject or the partner of a subject becomes pregnant during the study, the subject will be withdrawn from the study and followed through conclusion of the pregnancy (see [Section 9.7.5](#)).

When possible, a decision to discontinue a subject from the study should first be discussed with the Sponsor's Medical Monitor. If a subject is prematurely discontinued after randomization and prior to the final scheduled visit, every effort should be made to perform all of the Visit 8 assessments (Table 1). The reason(s) for early withdrawal must be recorded in the eCRF. Subjects withdrawn from the study will not be replaced.

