8. SUMMARY OF STUDY DATA

8.1. Subject Disposition

A summary of the analysis sets includes the number and percentage of subjects screened (rollover and de novo) and in the safety population. All percentages will be based on the number of subjects screened.

End of trial information will also be summarized in this table, including the number of subjects completing the study and the number of subjects who prematurely discontinued the study with reasons for withdrawal. All percentages will be based on the number of subjects screened.

A by-subject data listing of study completion information including the reason for premature study withdrawal, if applicable, will be presented.

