10. SAFETY ANALYSES

10.1. Adverse Events

The number and percent of subjects with any treatment-emergent adverse events (TEAEs) will be displayed by system organ class and preferred term (MedDRA Version 20.1). Within each preferred term, subjects will be counted only once if they had more than one event reported during the treatment period.

TEAEs will also be summarized by greatest reported severity for each event preferred term. Counts indicate subjects reporting one or more TEAEs that map to the severity grade classification for each preferred term. At each level of summarization (system organ class or event preferred term) subjects are only counted once and the worst severity case of repeated instances of the same TEAE will be used in tabulations. TEAEs will also be summarized by strongest investigator assessment of relationship to study drug in a similar manner.

In addition to the above described analyses, specific AE summaries will be presented under the following conditions:

- TEAEs by SOC/PT will be presented by modal dose within period (titration/dose response, maintenance, and taper period).

- TEAEs by SOC/PT will be presented by dose the subject was on at time of event within period (titration/dose response, maintenance, and taper period).
- All AE summaries will be presented by dose the subject was on at time of event.

Analyses of AEs will be performed for those events that are considered treatment emergent, where treatment emergent is defined as any AE with onset or worsening on or after the first dose of study drug up until last dose of study drug.

Treatment emergent summarization will be characterized by serious or not, the severity and the relationship with the study drug. A conservative approach will be taken to assess the relationship of an AE to study drug; if the relationship of an event is missing, it will be considered treatment-related. Missing severity will be coded as severe.

All TEAEs will be listed individually by subject. In addition, a separate listing will be produced for AEs that are not treatment-emergent.

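### The Safety population drops dosed subjects who attend no later visit, and completion and discontinuation percentages are taken over all screened subjects instead of treated subjects

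*SAP*

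**What the plan says.** **Safety population.** SAP 7.1.2: "Includes all subjects who receive at least one dose of open-label study treatment and have at least one post-dose visit". Protocol 11.2 has the same definition. Both documents use this set for all safety and efficacy analyses, and protocol 11.5 repeats that "Safety endpoints will be reported on the Safety population". SAP 7.1 defines only one other population, the screened one.

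**Early withdrawal.** Protocol Table 1, footnote 2, says that after premature withdrawal "all evaluations described under Visit 8/Week 60 (Final Visit) must be performed". Protocol 12.4 is softer: "every effort should be made to perform all of the Visit 8 assessments". It also lists loss to follow-up as a reason for withdrawal: "Confirmed at minimum by two phone calls and a traceable letter without answer".

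**Treatment-emergent events.** SAP 10.1 counts "any AE with onset or worsening on or after the first dose of study drug up until last dose of study drug".

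**Disposition.** SAP 8.1 puts screened subjects, the Safety population, completers and premature discontinuations with reasons in one table. Directly after the completion and discontinuation counts it states: "All percentages will be based on the number of subjects screened". Screened means everyone who consented. SAP 7.1.1: "The screening population will include the total number of subjects who were considered for this study", whether or not they took part. SAP 7.4.1 presents tables by modal dose (40, 60, 80 mg) and Overall unless otherwise specified.

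**The concern.** A safety set should contain everyone exposed. Here exposure starts at Baseline, where the site gives the first dose (protocol 6.2). The first scheduled visit after that is Week 2 (±3 days), once the 9-day titration is over. The subject most exposed to exclusion is therefore one who stops during titration and does not come back. That person may have stopped because of an adverse event, and SAP 10.1 plans separate tables for the titration period.

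The disposition rule is a separate fault. A consented subject who is never dosed cannot complete or discontinue treatment, yet sits in the denominator of both percentages. Such a subject also has no modal dose, so the default dose columns have no place for them.

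SAP 7.4.1 plans no statistical tests. The descriptive percentages are the findings on the primary objective, so their denominators matter.

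**Working it through.** The plan states no figure to reproduce. The documents give no rate of dosed subjects without a later visit, no event rate and no screen-failure rate. From the documents: about 300 enrolled (protocol 11.3, SAP 6) and up to 50 *de novo* subjects (SAP 6; the current protocol states no cap). Every other input below is an assumption.

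**(a) Post-dose visit condition**

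Let *N* = 300 dosed, *k* = subjects with no later visit, *E* = 45 subjects with an adverse event leading to discontinuation among those with a later visit, and *x* = subjects with such an event among the *k*.

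- Table shows: *E*/(*N* − *k*)
- All treated: (*E* + *x*)/*N*
- The two agree when *x* = *k* × *E*/(*N* − *k*)

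| *k* | Table shows | All treated | Break-even *x* |
|---|---|---|---|
| 1 | 45/299 = 15.1% | *x* = 0: 45/300 = 15.0%; *x* = 1: 46/300 = 15.3% | 1 × 45/299 = 0.15 |
| 3 | 45/297 = 15.2% | *x* = 0: 15.0%; *x* = 1: 15.3%; *x* = 3: 48/300 = 16.0% | 3 × 45/297 = 0.45 |

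The number of subjects with an event can only stay the same or fall. The percentage can move either way. It is too low if non-returners have a higher recorded on-treatment event rate than the rest, and slightly too high if nothing is recorded for them.

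Rare event: if the only treatment-emergent serious event falls in the only non-returner, 1/300 = 0.33% becomes 0/299, and SAP 11.2 prints a zero percentage as a blank.

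**(b) Screened denominator**

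Let *T* = 300 treated and *S* = screened. Shown percentage = treated percentage × *T*/*S*. Assume 90 discontinue (90/300 = 30.0%) and 210 complete (210/300 = 70.0%). Assume also that 250 rollover subjects all enter, 50 *de novo* subjects are enrolled, and only *de novo* subjects fail screening.

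| *De novo* screened | *De novo* failure | *S* | *T*/*S* | Discontinued | Completed |
|---|---|---|---|---|---|
| 56 | 6/56 = 10.7% | 306 | 0.980 | 90/306 = 29.4% | 210/306 = 68.6% |
| 63 | 13/63 = 20.6% | 313 | 0.958 | 90/313 = 28.8% | 210/313 = 67.1% |
| 83 | 33/83 = 39.8% | 333 | 0.901 | 90/333 = 27.0% | 210/333 = 63.1% |

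Rollover subjects can also fail eligibility (protocol 5.2, criteria 12 and 13), which would widen the gap. If 20% of all consented subjects failed, *S* = 300/0.80 = 375, and the figures would be 90/375 = 24.0% and 210/375 = 56.0%. With no screen failures the two denominators agree.

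**The case against.** The case for leaving the plan alone has several parts.

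- **The excluded group is very narrow.** Protocol 6.6 asks every withdrawing subject for the final-visit assessments, and anyone who attends stays in the set. This stands as a limit on size. It does not empty the group, because protocol 12.4 allows for subjects who never respond.
- **Silent subjects mostly have no recorded event.** Adding them would then lower the incidence. This is right, and it is why the direction is undetermined. It does not justify the exclusion: events can reach the site without a visit, and protocol 9.7.3 requires serious ones to be reported within 24 hours of the site learning of them.
- **A visit might include a telephone or unscheduled contact.** The term is undefined, and protocol Table 1 does list a telephone visit. A broad reading shrinks the group but does not help a subject with no contact that counts as a visit.
- **Serious cases are reported elsewhere.** Listings cover all data, and deaths and treatment-emergent serious events get narratives. True, but neither supplies an incidence.
- **The disposition point is presentational.** Counts and the Safety population size are in the same table, so a reader can largely recompute, and events leading to discontinuation have their own table on the Safety population. This softens the point. The printed percentages still do not describe treated subjects, and protocol 11.5 places disposition under its safety endpoints heading.
- **Dose columns are only a default, and there is an Overall column.** Correct, but SAP 8.1 specifies no other layout.

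**Conclusion.** Both rules are wrong as written. Followed exactly, SAP 7.1.2 and protocol 11.2 remove dosed non-returners from the incidence tables, and SAP 8.1 multiplies every completion and discontinuation percentage by treated/screened.

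The likely effect is modest. For a common event with one to three non-returners out of 300, the shift runs from about 0.2 points too high (15.2% against 15.0%) to 0.8 points too low (15.2% against 16.0%). For a rare serious event, the only case can vanish from the table, though it stays in the listing and narrative. Discontinuation is understated by 0.6, 1.2 or 3.0 points in the *de novo* scenarios, and completion by 1.4, 2.9 or 6.9 points. All of these depend on assumed rates. What does not depend on them is that neither set of percentages refers to all treated subjects once a dosed subject fails to return or a consented subject is not dosed. The point should be fixed because it touches the primary objective and is cheap to correct.

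**What to change.** 1. In SAP 7.1.2 and protocol 11.2, define the Safety population as all subjects who take at least one dose of open-label study drug, and delete the visit condition.
2. Add a disposition row for subjects dosed with no post-dose visit.
3. Add conventions for these subjects, since SAP 7.3.2.1 imputes dates only for adverse events and concomitant medications. If the last-dose date is unknown, count an event with onset on or after first dose as treatment-emergent and flag it. If modal dose or dose at event cannot be determined, count the subject under Overall and in a dose-unknown category.
4. Keep efficacy change scores limited to subjects with data.
5. In SAP 8.1, use screened subjects as denominator only for the screening and enrolment rows. Show screen failures on their own row, not as discontinuations, and base completion, discontinuation and reasons on treated subjects.

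**Cost.** A SAP revision and a short protocol amendment, which protocol 12.2 makes subject to Sponsor and IRB/IEC approval. The disposition change needs only the SAP, because the protocol sets no denominator. No new data are collected. Non-returners with no recorded event add to the denominator only, which the row in item 2 makes visible, and the dose tables may gain a dose-unknown category. Item 3 is useful but secondary; items 1 and 5 carry the correction.
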